4.3.5 Criteria to Resume Treatment

Subsequent dosing with study therapy may resume once drug-related non-DLT AEs resolve to Grade 1 or baseline.

Subjects experiencing AEs not meeting criteria for permanent discontinuation as outlined in [Section 4.3.6](#) may resume treatment with study medication under the following criteria:

- Subjects may resume treatment with study drug when the drug-related AE(s) resolve to Grade ≤ 1 or baseline value with the following exceptions:
 - Subjects may resume treatment in the presence of Grade 2 fatigue;
 - Subjects who have not experienced a Grade 3 drug-related skin AE may resume treatment in the presence of Grade 2 skin toxicity;
 - Subjects with Grade 2 uveitis or eye pain or blurred vision not meeting DLT criteria ([Section 4.3.1](#)) must resolve to baseline prior to resuming study therapy;
 - Drug-related pulmonary toxicity, diarrhea, or colitis, must have resolved to baseline before treatment is resumed;
 - Drug-related endocrinopathies adequately controlled with only physiologic hormone replacement may resume treatment.

If the criteria to resume treatment are met, the subject should restart treatment at the next scheduled time point per protocol.

The consideration to re-initiate study therapy under these exceptions will be made on a case by case basis after considering the overall benefit/risk profile and in consultation between the Investigator and the study sponsor. Any AE with clinical risk will be assessed on a case by case basis with the Investigator and the BMS Medical Monitor to determine the risks and benefits of continuing on therapy following resolution versus discontinuing therapy permanently.

If treatment with study medication is delayed > 6 weeks, the subject must be permanently discontinued from study therapy, except as specified in Section 4.3.6.

4.3.6 Guidelines for Permanent Discontinuation

Subjects will be required to permanently discontinue both study drugs for the following AEs:

- Any drug related AE occurring at any time that meets DLT criteria as outlined in [Section 4.3.1](#) will require permanent discontinuation with the following **exceptions**:
 - a) Grade 3 diarrhea, nausea, vomiting, or abdominal pain that returns to grade 1 or baseline within 3 days with medical intervention;
 - b) Grade 3 pruritus or rash that returns to grade 1 or baseline within 7 days or baseline with medical intervention;
 - c) Grade 4 electrolyte abnormalities that \leq 72 hours in duration;
 - d) Grade 4 neutropenia \leq 5 days in duration;
 - e) Grade 4 increase in amylase or lipase that is not associated with clinical or radiographic evidence of pancreatitis;
 - f) Grade 4 lymphopenia \leq 5 days in duration.
- Any dosing delay lasting > 6 weeks will be cause for permanent discontinuation. Extensions to the period of dose delays may be granted for individual subjects on a case by case basis after specific consultation and agreement between the Investigator and BMS Medical Monitor in settings where benefit/risk may justify continued study therapy (e.g., subject deriving clinical benefit who requires prolonged steroid taper for management of non-DLT irAEs, or experiences delays for management of a non-drug-related AE).
- Accordingly, dosing delays to allow for prolonged steroid tapers to manage drug-related AEs are allowed. Additionally, dosing delays > 6 weeks that occur for non-drug-related reasons may be allowed if approved by the BMS Medical Monitor.
- Prior to re-initiating treatment in a subject with a dosing delay lasting > 6 weeks, the BMS Medical Monitor must be consulted.
- Tumor assessments should continue as per protocol even if dosing is delayed.

All subjects who discontinue IP should comply with protocol specified follow-up procedures as outlined in [Section 3.3](#). The only exception to this requirement is when a subject withdraws consent for all study procedures including post-treatment study follow-up or loses the ability to consent freely (e.g., is imprisoned or involuntarily incarcerated for the treatment of either a psychiatric or physical illness).

If study treatment is discontinued prior to the subject's completion of the study, the reason for the discontinuation must be documented in the subject's medical records and entered on the appropriate CRF page.

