4.3.1 Dose-limiting Toxicities

AEs will be graded according to the NCI CTCAE v4.03.

Non-hematologic Dose-limiting Toxicity (DLT)

A. Hepatic Non-hematologic DLT

Any one of the following study drug-related events will be considered a hepatic DLT:

- Any Grade ≥ 3 elevation of AST, ALT, or total bilirubin
- Grade 2 AST or ALT with symptomatic liver inflammation (e.g., right upper quadrant tenderness, jaundice, pruritus)
- AST or ALT $> 3 \times$ ULN and concurrent total bilirubin $> 2 \times$ ULN without initial findings of cholestasis (elevated serum ALP (e.g., findings consistent with Hy's law or FDA definition of potential drug-induced liver injury or pDILI). Note that this special category of DLT uses ULN rather than CTC Grade for definition

B. Non-hepatic Non-hematologic DLT

Any of the following events will be considered a Non-Hepatic Non-Hematologic DLT:

- Any Grade 2 drug-related uveitis or eye pain or blurred vision that does not respond to topical therapy and does not improve to Grade 1 severity ≤ 2 weeks OR requires systemic treatment
- Grade 3 drug-related uveitis, pneumonitis, bronchospasm, neurologic toxicity, hypersensitivity reaction, or infusion reaction of any duration requires discontinuation
- Any Grade 3 or greater non-dermatologic, non-hepatic non-hematologic study drug-related toxicity will be considered a dose-limiting toxicity with the following specific EXCEPTIONS:
 - Grade 3 or grade 4 electrolyte abnormalities that are not complicated by associated clinical adverse experiences, last ≤ 48 hours and either resolve spontaneously or respond to conventional medical intervention
 - Grade 3 nausea, vomiting or diarrhea that lasts less than 48 hours, and either resolves spontaneously or responds to conventional medical intervention
 - Isolated Grade 3 elevation of amylase or lipase not associated with clinical or radiographic evidence of pancreatitis
 - Isolated Grade 3 fever not associated with hemodynamic compromise (eg, hypotension, clinical or laboratory evidence of impaired end-organ perfusion)
 - Grade 3 endocrinopathy that is well controlled by hormone replacement
 - Grade 3 tumor flare (defined as pain, irritation, or rash that localizes to sites of known or suspected tumor)
 - Grade 3 fatigue for ≤ 7 days
 - Grade 3 infusion reaction that returns to Grade 1 in ≤ 6 hours

C. Dermatologic DLT

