- Grade 3/4 rash if no improvement (i.e. resolution to \leq Grade 1) after a 1-2 week infusion delay. Subjects who have not experienced a Grade 3 drug-related skin AE may resume treatment in the presence of Grade 2 skin toxicity.

D. Hematologic DLT (Study Drug-related)

- Grade 4 neutropenia \geq 5 days in duration
- Grade 4 thrombocytopenia or Grade 3 thrombocytopenia with clinically significant bleeding, or any requirement for platelet transfusion
- Grade 4 anemia not explained by underlying disease
- Grade 4 febrile neutropenia
- Grade 3 febrile neutropenia that lasts > 48 hours
- Grade \geq 3 hemolysis (ie, requiring transfusion or medical intervention such as steroids)

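### For an electrolyte DLT lasting up to 72 hours, Sections 4.3.1 B and 4.3.6 together mandate permanent discontinuation at Grade 3 but exempt Grade 4

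*Combined protocol and SAP*

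**What the plan says.** Two sections of the protocol act in sequence.

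**Section 4.3.1 B (definition of a DLT).** The starting rule is broad: "Any Grade 3 or greater non-dermatologic, non-hepatic non-hematologic study drug-related toxicity will be considered a dose-limiting toxicity with the following specific EXCEPTIONS". The electrolyte exclusion covers "Grade 3 or grade 4 electrolyte abnormalities that are not complicated by associated clinical adverse experiences", provided that they last no more than "48 hours and either resolve spontaneously or respond to conventional medical intervention". All three conditions must hold, and both grades are treated the same.

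**Section 4.3.6 (permanent discontinuation).** Both study drugs must be stopped permanently for "Any drug related AE occurring at any time that meets DLT criteria as outlined in" Section 4.3.1, with exceptions (a) to (f). Exception (c) is the only one for electrolytes. It covers "Grade 4 electrolyte abnormalities that" are at most "72 hours in duration". It does not mention Grade 3, complications, or response to intervention.

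Section 3.6 refers to Section 4.3.6 for the decision to interrupt or discontinue and adds no rule for electrolytes.

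**The concern.** A list of exceptions to a stopping rule would be expected to be at least as lenient for a milder event as for a more severe one of the same kind and length. Here the order is reversed over part of the range. A site applying the text literally must permanently stop a subject with a Grade 3 electrolyte DLT, but is not required to stop a subject with a Grade 4 event of the same duration.

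The rule applies at any time on treatment, which can run to 13 cycles (Section 3.1). Sites that notice the mismatch may settle it in different ways, so similar events could be handled differently. Adverse events leading to discontinuation are also part of the safety assessment in Section 8.3.1, so an unclear stopping rule feeds into a reported summary.

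**Working it through.** No sample size, power or error rate is involved. The check applies the two rules in order to each kind of drug-related electrolyte event.

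**Rule 1 (Section 4.3.1 B).** For Grade 3 or 4: DLT = not (uncomplicated AND duration ≤ 48 h AND resolves or responds).

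**Rule 2 (Section 4.3.6).** Mandatory permanent stop = DLT AND not (Grade 4 AND duration ≤ 72 h).

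| Duration | Other conditions | DLT (either grade)? | Grade 3 | Grade 4 | Inverted? |
|---|---|---|---|---|---|
| ≤ 48 h | uncomplicated and resolves or responds | no | no mandate | no mandate | no |
| ≤ 48 h | complicated, or neither resolves nor responds | yes | mandatory stop | exempt under (c) | yes |
| > 48 h to 72 h | any | yes | mandatory stop | exempt under (c) | yes |
| > 72 h | any | yes | mandatory stop | mandatory stop | no |

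The rules were run at 24, 48, 60, 72 and 80 hours, with and without complications, and with and without response: 5 × 2 × 2 = 20 combinations for each grade. In 2 neither grade is a DLT, in 4 (all at 80 hours) both grades stop, and in 14 Grade 3 stops while Grade 4 is exempt (2 + 4 + 14 = 20). These counts describe the grid, not how often such events occur.

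**One case in full, at 60 hours.** An uncomplicated, responding Grade 3 event is a DLT because 60 > 48. No exception names it, so the stop is mandatory. A complicated Grade 4 event of the same length is also a DLT, but 60 ≤ 72, so exception (c) exempts it.

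**Does another section lift the Grade 3 mandate?**
- Section 4.3.4 requires drug to be held after any DLT. It permits resumption only for subjects who do not meet the permanent discontinuation rules.
- Section 4.3.5 sets the resumption criteria and a case-by-case review, again for events outside Section 4.3.6.
- The extension clause in Section 4.3.6 concerns the length of a dosing delay.
- Section 3.11 lets the investigator's judgement add a stop, not remove one.

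None of them does.

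**The other exceptions, for completeness.** In Section 4.3.1 D, "Grade 4 neutropenia" is a DLT at 5 days or more; exception (d) covers 5 days or fewer. The two meet only at exactly 5 days. Exception (f) covers "Grade 4 lymphopenia" of up to 5 days, but Section 4.3.1 D does not list lymphopenia as a DLT.

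**The case against.** **The two lists serve different purposes.** DLTs guide dose escalation, while discontinuation is subject management (Section 3.6), so the limits need not be equal. Exception (a) likewise allows 3 days where the DLT exclusion for nausea, vomiting or diarrhea uses less than 48 hours. An exception must in fact be wider than the DLT exclusion to have any effect. This stands: the gap between 48 and 72 hours is not in itself an error. It does not explain why the wider limit is given to Grade 4 alone.

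**Exception (c) might be read as including Grade 3.** The list does not support that. It names the grade item by item: Grade 3 in (a) and (b), Grade 4 in (c) to (f). Naming only Grade 4 works in (e), because isolated Grade 3 amylase or lipase elevation without pancreatitis is already outside the DLT definition. For electrolytes the Grade 3 exclusion is conditional, so Grade 3 DLTs exist and nothing covers them.

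**Safeguards remain on the Grade 4 side.** Drug is held (Section 4.3.4). Restart generally needs recovery to Grade 1 or baseline, and any event with clinical risk is reviewed with the Medical Monitor (Section 4.3.5). The investigator must stop treatment if continuing is not in the subject's interest (Section 3.11). A drug-related clinical complication may also be a DLT in its own right, which (c) does not cover. A reader might infer that a complicated Grade 4 subject is simply kept on drug and that the text therefore creates a safety hazard. These sections do not support that. The mandatory side of the inversion is also the cautious one.

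**Other stronger readings.** A reader might infer that every Grade 3 electrolyte event over 48 hours is treated more harshly than Grade 4. Above 72 hours it is not. A reader might also infer that the count of adverse events leading to discontinuation is distorted. The documents give no frequency for these events, that summary is descriptive, and no formal hypothesis is tested (Section 1.3), so no such effect is shown. Finally, (d) and (f) might seem to add wrong decisions. They do not: neutropenia has one clear outcome at every duration, and an exception for something that is not a DLT changes nothing.

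**Conclusion.** The concern holds within a defined window. For drug-related electrolyte abnormalities that meet DLT criteria (over 48 hours, complicated, or neither resolving nor responding) and last no more than 72 hours, Sections 4.3.1 B and 4.3.6 together mandate permanent discontinuation at Grade 3 and exempt Grade 4. Outside that window the grades are treated alike.

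This is an internal inconsistency with an inverted result, not evidence of harm or of a biased endpoint. Its practical size is unknown. The conclusion assumes that the exceptions mean the grades they name and that duration is counted the same way in both sections; neither section says whether it is time at that grade or the whole episode. The observations on (d) and (f) are editorial only.

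**What to change.** The sponsor should reconcile Section 4.3.1 B with exception (c) in Section 4.3.6 so that the electrolyte exception does not treat the lower grade more strictly than the higher one. The sponsor must choose the clinical limits (grades, durations, and any condition on complications or response); none is proposed here. One drafting check is needed: simply copying the Section 4.3.1 B conditions into (c) would leave it exempting only events that are not DLTs, and so doing nothing.

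In the same revision, (d) and (f) should be checked against Section 4.3.1 D as an editorial matter.

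The cost is wording in one list, with no added procedures, visits or data collection.

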4.3.7 Treatment of Drug-related Infusion Reactions

Since BMS-986156 and nivolumab contain only human immunoglobulin protein sequences, it is unlikely to be immunogenic and induce infusion or hypersensitivity reactions. However, if such a reaction were to occur, it might manifest with fever, chills, rigors, headache, rash, pruritus, arthralgias, hypo- or hypertension, bronchospasm, or other symptoms. All Grade 3 or 4 infusion

reactions should be reported within 24 hours to the BMS Medical Monitor and reported as an SAE if criteria are met. Infusion reactions should be graded according to NCI CTCAE v4.03 guidelines.

Treatment recommendations are provided below and may be modified based on local treatment standards and guidelines as appropriate:

For Grade 1 symptoms: (Mild reaction; infusion interruption not indicated; intervention not indicated)

Remain at bedside and monitor subject until recovery from symptoms. The following prophylactic premedications are recommended for future infusions: diphenhydramine 50 mg (or equivalent) and/or acetaminophen/paracetamol 325 to 1000 mg at least 30 minutes before additional study drug administrations.

For Grade 2 symptoms: Moderate reaction requires therapy or infusion interruption but responds promptly to symptomatic treatment [e.g., antihistamines, non-steroidal anti-inflammatory drugs, narcotics, corticosteroids, bronchodilators, IV fluids]; prophylactic medications indicated for ≤ 24 hours.

- Stop the nivolumab infusion, begin an IV infusion of normal saline, and treat the subject with diphenhydramine 50 mg IV (or equivalent) and/or paracetamol 325 to 1000 mg (acetaminophen); monitor subject until resolution of symptoms.
- Bronchodilator or corticosteroid therapy may also be administered as appropriate.
- The infusion may be restarted at 50% of the original infusion rate when symptoms resolve; if no further complications ensue after 30 minutes, the rate may be increased to 100% of the original infusion rate. Monitor subject closely.
- The amount of study drug infused must be recorded on the CRF.
- If symptoms recur, then no further nivolumab, as the case may be, will be administered at that visit.
- The following prophylactic premedications are recommended for future infusions: diphenhydramine 50 mg (or equivalent) and/or paracetamol 325 to 1000 mg (acetaminophen) should be administered at least 30 minutes before additional nivolumab administrations. If necessary, corticosteroids (up to 25 mg of SoluCortef or equivalent) may be used.

Late-occurring symptoms: In the case of late-occurring hypersensitivity symptoms (e.g., appearance of a localized or generalized pruritus within 1 week after treatment), symptomatic treatment may be given (eg, oral antihistamine, or corticosteroids).

For Grade 3 or Grade 4 symptoms (Severe reaction, Grade 3: prolonged [e.g., not rapidly responsive to symptomatic medication and/or brief interruption of infusion]; recurrence of symptoms following initial improvement; hospitalization indicated for other clinical sequelae [e.g., renal impairment, pulmonary infiltrates]; Grade 4: life-threatening; pressor or ventilatory support indicated).

Immediately discontinue study drug infusion. Begin an IV infusion of normal saline, and treat the subject as follows. Recommend bronchodilators, epinephrine 0.2 to 1 mg of a 1:1,000 solution for subcutaneous administration or 0.1 to 0.25 mg of a 1:10,000 solution injected slowly for IV administration, and/or diphenhydramine 50 mg IV with methylprednisolone 100 mg IV (or

equivalent), as needed. Subject should be monitored until the Investigator is comfortable that the symptoms will not recur. Study drug will be permanently discontinued. Investigators should follow their institutional guidelines for the treatment of anaphylaxis. Remain at bedside and monitor subject until recovery from symptoms. In the case of late-occurring hypersensitivity symptoms (e.g., appearance of a localized or generalized pruritus within 1 week after treatment), symptomatic treatment may be given (e.g., oral antihistamine, or corticosteroids).

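### The Grade 2 infusion-reaction bullets in Section 4.3.7 name only nivolumab, and the section is unclear whether a reaction that recurs on restart ends dosing for the visit or for good

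*Combined protocol and SAP*

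**What the plan says.** Section 4.3.7 opens by naming both antibodies and tells sites to grade infusion reactions by CTCAE v4.03. Its Grade 1 text recommends premedication "at least 30 minutes before additional study drug administrations", which covers either drug. The Grade 3/4 text also speaks of study drug in general.

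The Grade 2 text narrows to one drug in three places:

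- Stop: "Stop the nivolumab infusion, begin an IV infusion of normal saline".
- Recurrence after restart: "If symptoms recur, then no further nivolumab, as the case may be, will be administered at that visit".
- Premedication for later infusions: "should be administered at least 30 minutes before additional nivolumab administrations".

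Two other Grade 2 bullets, on restarting at half rate and on recording the amount infused, are not tied to nivolumab.

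For Grade 3, the section lists "recurrence of symptoms following initial improvement" as a criterion in its own right, and the action is "Study drug will be permanently discontinued". Grade 3 and 4 reactions must also be reported to the Medical Monitor within 24 hours.

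**The concern.** Section 1.6 treats infusion reactions to BMS-986156 in humans as a risk of unknown size and points to management guidance in the protocol as part of the mitigation. Section 4.3.2 lists seven adverse-event groups with management algorithms, and infusion reactions are not among them. In the documents as provided, Section 4.3.7 is therefore the guidance that Section 1.6 relies on. Its Grade 2 instructions leave out the investigational antibody that the guidance was meant to cover.

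The second issue is what follows a recurrence on restart. A site that stays with the Grade 2 bullet withholds drug for that visit and may then look to Section 4.3.5: "If the criteria to resume treatment are met, the subject should restart treatment at the next scheduled time point per protocol". A site that regrades the event to Grade 3 stops treatment permanently and reports within 24 hours. Whether the subject is re-exposed, and whether the sponsor is told promptly, depends on which lines the site reads.

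**Working it through.** No arithmetic applies. The check sets the instructions side by side.

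**Drug named**

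| Section 4.3.7 instruction | Drug named | Reaction to BMS-986156 in combination (B, D, E) | Monotherapy (A, C) |
|---|---|---|---|
| Grade 1 premedication | study drug | covered | covered |
| Grade 2 stop | nivolumab | not covered literally | not covered literally |
| Grade 2 restart | none | covered | covered |
| Grade 2 recurrence | nivolumab | not covered literally | not covered literally |
| Grade 2 premedication | nivolumab | covered in effect | not covered literally |
| Grade 3/4 action | study drug | covered | covered |

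The premedication row needs care. Under Section 3.1 nivolumab is infused first at combination visits, so premedication given before nivolumab also precedes BMS-986156. Only Parts A and C are left out. The result there is odd: a Grade 1 reactor on monotherapy has a premedication recommendation, and a Grade 2 reactor has none. The phrase *as the case may be* in the recurrence bullet makes sense only if a choice of drugs was intended, which suggests that a second name was lost.

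**Recurrence on restart**

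1. A Grade 2 reaction resolves and the infusion is restarted at half rate. Symptoms return.
2. The Grade 2 recurrence bullet ends dosing for that visit and is silent on later visits.
3. The event also fits the Grade 3 wording, "recurrence of symptoms following initial improvement", for which "Study drug will be permanently discontinued". That action has no time exception.
4. Section 4.3.1 points the same way in one bullet: for Grade 3 it says "hypersensitivity reaction, or infusion reaction of any duration requires discontinuation".
5. The next bullet of Section 4.3.1 excepts from the DLT definition a Grade 3 infusion reaction that is back to Grade 1 within 6 hours. Section 4.3.6 ties required discontinuation to events meeting DLT criteria. A recurrence that settles within 6 hours could therefore be read as not requiring discontinuation under Section 4.3.6, although Section 4.3.7 and the bullet in step 4 say that it does.
6. Section 4.3.5 allows non-DLT drug-related events to resume dosing on resolution. It also sends any event with clinical risk to case-by-case review by the investigator and the Medical Monitor.

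Steps 3 and 4 favour discontinuation. Step 5 leaves a route around it, and nothing in the Grade 2 bullet directs the reader to the Grade 3 text.

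**The case against.** The strongest reply is that the recurrence text is not contradictory. Grading by CTCAE comes first, recurrence after improvement is Grade 3, and the Grade 2 bullet gives only the bedside action for that day. A site can give no more drug at the visit and then discontinue permanently, so both instructions are followed. This largely stands, and it is why the point is put as lack of clarity. What remains is that the bullet sits under Grade 2, limits its consequence to one visit, and is followed by premedication advice for future infusions, so a reader has reason to expect re-dosing.

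On drug naming, a reader might infer that a monotherapy infusion would be left running through a Grade 2 reaction. The documents do not support that. The Grade 2 definition itself refers to therapy or interruption of the infusion, the restart bullet is drug-neutral, and the section allows local modification. Preparation and administration instructions also come in separate site materials, which may be clearer.

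A reader might also infer that two sites could act in opposite ways with no check. The Medical Monitor review in Section 4.3.5 and the 24-hour report for Grade 3 and 4 reactions both weigh against that, though the report is triggered only once a site has graded the event as 3.

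**Conclusion.** The Grade 2 bullets are wrong as written, and the severity is minor. Three bullets name one drug in a section written for two. Read literally, two of them miss reactions to BMS-986156 in every part, and all three miss Parts A and C. On recurrence after restart, the better reading is Grade 3 with permanent discontinuation, but the Grade 2 bullet does not say so, and the 6-hour exception in Section 4.3.1 combined with Section 4.3.6 leaves the matter open.

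No number of affected subjects or doses is claimed. The safety update in Section 1.6 counts infusion reactions but does not give the number that recurred on restart, and the documents do not state how many monotherapy subjects were still being dosed under this revision. A reader might infer an effect on DLT counts or efficacy results. Nothing in the documents shows one. The conclusion rests only on the wording of Sections 4.3.1, 4.3.5, 4.3.6 and 4.3.7 as provided.

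**What to change.** 1. In the Grade 2 stop and recurrence bullets, replace nivolumab with *the study drug being infused (BMS-986156 or nivolumab)*.
2. In the Grade 2 premedication bullet, use the Grade 1 wording: "at least 30 minutes before additional study drug administrations".
3. Add to the recurrence bullet: *Recurrence after initial improvement meets the Grade 3 definition; manage under the Grade 3/4 text, including permanent discontinuation and the 24-hour report to the Medical Monitor.*
4. State in Sections 4.3.1 and 4.3.6 that the 6-hour exception applies to DLT classification only and does not permit re-dosing. If the sponsor does intend re-dosing, amend the Grade 3 text in Section 4.3.7 and the discontinuation bullet in Section 4.3.1 to match.

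The cost is a few words in three bullets, one added sentence, a clarification in two sections and a notice to sites. No procedures, subjects or analyses are added.
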